9.1 Integrated Correlative Studies

9.1.1 PD-L1 expression,

PD-L1 expression has demonstrated variable utility as a predictive marker in the setting of immune checkpoint blockade and may be impacted by local radiotherapy. We hypothesize that there will be a correlation between PD-L1 expression levels and response as well as a potential increase in the setting of localized radiotherapy. Similarly, we predict that increased T-cell infiltration into the tumor microenvironment will predict for response to therapy.

9.1.1.1 Collection and Handling of Specimen(s)

Immunohistochemical staining of PD-L1, CD3, CD4 and CD8 will be used as integrated markers in the clinical trial, which could be used in future trials to identify a group of patients who would have a good response to the treatment as a stratification variable. Tumor specimens will be collected at baseline in patients enrolled on both cohorts. Pre-treatment archived specimens will

be retrieved if no fresher tissue can be obtained prior to treatment initiation on day 1. Post-treatment tissues will be collected and fixed by 10% neutral buffered formalin overnight, dehydrated and paraffin embedded. Four-micrometer-thick sections will be cut. The paraffin blocks and unstained slides will be stored at room temperature. All IF staining will be performed in the Center for Immuno-Oncology Pathology Core at Dana-Farber/Harvard Cancer Center Specialized Histopathology Core, which will be a central research laboratory for this multiple-center clinical trial. Unstained slides from other centers will be shipped to [name], [name], Brigham and Women Hospital, [name], [name].

9.1.1.2 Site(s) Performing Correlative Study

Laboratory information

The IHC staining will be conducted in the DFCI CIMAC Tissue Biomarker Lab, a research laboratory with GLP standard by [name], who is a hematopathologist at the Brigham and Women's hospital with prior expertise evaluating PD1, PDL1 and other immunologic markers in paraffin embedded tumor samples [92].

9.2 Exploratory/Ancillary Correlative Studies

9.2.1 Monitoring Peripheral Blood for Changes in Immune Function

Correlative sciences will be expanded from our previously determined biology of patients treated with both radiation and immune checkpoint blockade. Subpopulations of PBMCs will be isolated, including but not limited to dendritic cells, T cells, B cells, and CD4+Ki67+, CD8+Ki67+, CD4+ICOS+, CD8+ICOS+. populations. Phenotype changes in these cell populations by CyTOF will be determined as a function of treatment. These include regulatory and effector immune panels, naïve and memory CD4, CD8 and NK lymphocyte populations. Given its importance in immune regulation and association, we will evaluate Tie-2 expressing monocytes (TEM).

9.2.1.1 Collection and handling of Specimen(s)

Serial blood/plasma samples will be collected at baseline and then prior to cycle 2. A panel of cytokines and chemokines will be tested in plasma using Olink. Absolute lymphocyte count (ALC) will be monitored.

Peripheral blood mononuclear cells (PBMCs) will be collected from whole blood to assess immune cell populations. PBMCs will be cryoforzen and plasma will be snap frozen for batched analysis. CyTOF will be performed in order to identify different T cell populations, their activation status, and the production of different cytokines as well as other immune cell populations

9.2.1.2 Site(s) Performing Correlative Study

Laboratory information

CyTOF will be performed by the DFCI CIMAC Immune Assessment Lab led by [name], [name] and [name]. Olink will be performed at the Mt. Sinai CIMAC led by [name].

9.2.2 Spatial quantification of the tumor microenvironment

We hypothesize that co localization of multiple immune markers including PD-L1, PD-L2, PD-1, CD3, and CD8 will be associated with favorable response. We also predict that in the colorectal cohort, these factors will be influenced by either low or high-dose radiation.

9.2.2.1 Site(s) Performing Correlative Study

Laboratory information

The IF staining will be conducted in the DFCI CIMAC Tissue Biomarker Lab, a research laboratory with GLP standard under the direction of [name] a hematopathologist at the Brigham and Women's hospital with prior expertise evaluating PD1, PDL1 and other immunologic markers in paraffin embedded tumor samples [92].

9.2.3 Sequencing of DNA and RNA

Previous studies have suggested that mutational burden may predict for response among patients treated with PD-1 or CTLA-4 inhibitors. Tissue collected from mandatory biopsies in conjunction with sequencing performed on peripheral blood will determine mutational burden to correlate with response and also RNA expression to better correlate the tumor microenvironment and associate with IHC and IF protein expression data.

9.2.3.1 Collection and handling of Specimen(s)

Tumor specimens will be collected at baseline in patients enrolled on both cohorts. Pre treatment archived specimens will be retrieved if no fresher tissue can be obtained prior to treatment initiation on day 1. Post treatment tissues will be collected and fixed by 10% neutral buffered formalin overnight, dehydrated and paraffin embedded. Four-micrometer-thick sections will be cut. The paraffin blocks and unstained slides will be stored at room temperature.

9.2.3.2 Site(s) Performing Correlative Study

Laboratory information

The sequencing will be conducted in the DFCI CIMAC Translational Immunogenomics Lab and UC Davis Comprehensive Cancer Center under the direction of [name], a research

laboratory under the direction of [name] and [name] have extensive prior experience evaluating sequencing and RNA expression data.

9.3. Electronic Collection of PRO-CTCAE data

Site users of ePRO and the Patient Cloud require the same access as those using Rave. Access to the trial in the Patient Cloud is granted through the iMedidata application to all persons with the appropriate roles assigned in Regulatory Support System (RSS).

Site users are referred to the [Medidata Learning Tool](#) for reference information on Patient Cloud ePRO for CRAs.

Patient will view the survey questions on his/her device. The patient will have a window of 48 hours to complete the survey. Once the patient hits the submit button, the questions will no longer be on his/her device and will be directly sent to the RAVE database and available to the site CRAs for compliance monitoring.

10. STUDY CALENDAR

Baseline evaluations are to be conducted within 4 weeks prior to start of protocol therapy. Scans and x-rays must be done ≤5 weeks prior to the start of therapy. In the event that the patient’s condition is deteriorating, laboratory evaluations should be repeated within 48 hours prior to initiation of the next cycle of therapy. Note that all study visits in the calendar are specified by week, but should be performed on the same day of the week when feasible and every effort should be made to schedule them +/-2 days.

Cohort 1 – Non small cell lung cancer

	Pre- Study	Wk 1	Wk 2	Wk 3	Wk 4	Wk 5	Wk 6	Wk 7	Wk 8	Wk 9	Wk 10	Wk 11	Wk 12	Wk 13- 52	Off Treatment ^e
MEDI4736(durvalumab)		A				A				A				A ^e	
Tremelimumab		B				B				B				B ^e	
Radiation therapy			C				C				C			C ^e	
Informed consent	X														
Demographics	X														
AE/SAE Assessments ^m		X				X				X				X ^e	X
Medical history	X	X				X				X				X ^e	
Concurrent meds ^d	X													X	X
Physical exam	X	X				X				X				X ^e	X
Vital signs ^p	X	X				X				X				X ^e	X
Performance status	X	X				X				X				X ^e	X
CBC w/diff, plts	X	X ^k				X				X				X ^e	X
Serum chemistry ^a	X	X ^k				X				X				X ^e	X
EKG ^j	X														
Hepatitis B and C and HIV ⁿ	X														
Urinalysis	X ⁱ														
Tumor measurements	X		Tumor measurements should be performed during week 7 or 8 and then repeated every 12 weeks +/- 5 days. Documentation (radiologic) must be provided for patients removed from study for progressive disease.												
Radiologic evaluation ^l	X		Radiologic measurements should be performed during week 7 or 8 and then every 12 weeks +/- 5 days while on treatment .												X ^o
B-HCG	X ^b	X				X				X				X ^e	X ^e
Head MRI ^{dh}	X													X ^d	
Research blood samples	X					X									
Biopsy of site(s) of disease	X ^f							X ^g							
PRO-CTCAEⁿ	X		X		X		X		X				X	X	X

	
A: MEDI4736(durvalumab): Administered intravenously at a dose of 1500mg every 4 weeks for a maximum of 13 doses.
 
B: Tremelimumab: Administered intravenously at a dose of 75mg every 4 weeks for a maximum of 4 doses.
 
C: Radiation therapy: Administered only on week 2 for Arm A (high dose radiation) and every 4 weeks for a maximum of 4 times in Arm B (low dose radiation)
 
a: Albumin, alkaline phosphatase, total bilirubin, bicarbonate, BUN, calcium, chloride, creatinine, glucose, LDH, phosphorus, potassium, total protein, SGOT [AST], SGPT [ALT], sodium. Also amylase, creatinine clearance, gamma glutamyltransferase, lipase, and magnesium, CPK, TSH. Free T3 or free T4 also measured if TSH is abnormal or if there is clinical suspicion of an AE related to the endocrine system. .
 
b: Serum pregnancy test (women of childbearing potential). Women of child-bearing potential must have a negative serum beta-HCG pregnancy test during screening and a negative urine beta-HCG pregnancy test within 24 hours of starting treatment.
 
c: Every 12 weeks during weeks 12-52 and then 30,60, 90 days after discontinuation
 
d: Every 12 weeks
 
e: Every 4 weeks
 
f: Archival tissue may be used in place of biopsy in this cohort.
 
g: To be performed week 7 or 8. Optional in patients with irradiated lesions outside the liver. For patients who receive radiation to the liver, this second biopsy is required unless unsafe to perform.
 
h: Head CT may be substituted for MRI if patient cannot tolerate MRI. Subsequent MRI's to be performed only if previously treated brain metastases or when clinically indicated.
 
i: At baseline (screening) and then as clinically indicated.
 
j: Abnormal findings should be repeated and require appropriate clinical evaluation. Normal EKGs do not require repeating.
 
k: If screening laboratory assessments are performed within 3 days prior to Day 1 (first infusion day), they do not need to be repeated at Day 1
 
l: CT Chest, Abdomen, and Pelvis (CAP)
 
m: During scheduled history and physical exams and during monitoring of AE's, attention should be paid to the side effects resulting from radiation and any potential enhancement of these due to the administration of immunotherapy.
 
n: Negative serologies over the preceding year may replace screening study
 
o: when off treatment for reasons other than progression after week 7-8, until week 52.
 
p: Vital signs timepoints for infusions are pre-dose, every 30 minutes; post-dose 30 and 60 minutes (+/- 10 minutes)
 
q: PRO-CTCAE items to be completed at baseline, every 2 weeks for 8 weeks and then every 4 weeks for a total of 8 cycles. All patients on any arm of study will answer the same list of PRO-CTCAE questions.

--	---

The following visits and assessments are required after discontinuing study treatment:

Days following discontinuation:

30, 60 and 90 days (+/-5 days): physical exam, vital signs, body weight, CBC with diff, serum chemistries^a, pregnancy test for WOCB (urine or serum) AE/SAE assessments, concurrent medications, and performance status

Cohort 2 – Colorectal cancer

	Pre- Study	Wk 1	Wk 2	Wk 3	Wk 4	Wk 5	Wk 6	Wk 7	Wk 8	Wk 9	Wk 10	Wk 11	Wk 12	Wk 13- 52	Off Treatment ^e
MEDI4736(durvalumab)		A				A				A				A	
Tremelimumab		B				B				B				B	
Radiation therapy			C				C				C			C	
Informed consent	X														
Demographics	X														
AE/SAE Assessments ^l	X	X				X				X				X ^e	X
Medical history	X	X				X				X				X ^e	
Concurrent meds ^d	X													X	
Physical exam	X	X				X				X				X ^e	X
Vital signs ^p	X	X				X				X				X ^e	X

Performance status	X	X				X				X				X ^e	X
CBC w/diff, plts	X	X ^b				X				X				X ^e	X
Serum chemistry ^a	X	X ^b				X				X				X ^e	X
EKG ^f	X														
Hepatitis B and C and HIV ^m	X														
Urinalysis	X ^f														
Tumor measurements	X		Tumor measurements should be performed during week 7-8 and then repeated every 12 weeks +/- 5 days. Documentation (radiologic) must be provided for patients removed from study for progressive disease.												
Radiologic evaluation ^k	X		Radiologic measurements should be performed during week 7 or 8 and then every 12 weeks +/- 5 days while on treatment.												X ^e
B-HCG	X ^b	X				X				X				X ^e	X ^e
Research blood samples	X					X									
Biopsy of site(s) of disease	X ⁱ								X ^j						
PRO-CTCAE ⁿ	X		X		X		X		X				X	X	X

A: MEDI4736(durvalumab): Administered intravenously at a dose of 1500mg every 4 weeks for a maximum of 13 doses.
 
B: Tremelimumab: Administered intravenously at a dose of 75mg every 4 weeks for a maximum of 4 doses.
 
C: Radiation therapy: Administered only on week 2 for Arm A (high dose radiation) and every 4 weeks for a maximum of 4 times in ARM B (low dose radiation)
 
a: Albumin, alkaline phosphatase, total bilirubin, bicarbonate, BUN, calcium, chloride, creatinine, glucose, LDH, phosphorus, potassium, total protein, SGOT [AST], SGPT [ALT], sodium. Also Also amylase, creatinine clearance, gamma glutamyltransferase, lipase, and magnesium,CPK, TSH. Free T3 or free T4 also measured if TSH is abnormal or if there is clinical suspicion of an AE related to the endocrine system..
 
b: Serum pregnancy test (women of childbearing potential). Women of child-bearing potential must have a negative serum beta-HCG pregnancy test during screening and a negative urinebeta-HCG pregnancy test within 24 hours of starting treatment.
 
c: Every 12 weeks during weeks 12-52 and then 30,60, 90 days after discontinuation
 
d: Every 12 weeks
 
e: Every 4 weeks
 
f: At baseline (screening) and then as clinically indicated.
 
g: Abnormal findings should be repeated and require appropriate clinical evaluation.Normal EKGs do not require repeating.
 
h: If screening laboratory assessments are performed within 3 days prior to Day 1 (first infusion day), they do not need to be repeated at Day 1.
 
i: Archival tissue may be used in place of biopsy in this cohort.
 
j: To be performed week 7 or 8. Optional in patients with irradiated lesions outside the liver. For patients who receive radiation to the liver, this second biopsy is required unless unsafe to perform.
 
k: CT Chest, Abdomen, and Pelvis (CAP)
 
l: During scheduled history and physical exams and during monitoring of AE's, attention should be paid to the side effects resulting from radiation and any potential enhancement of these due to the administration of immunotherapy.
 
m: Negative serologies over the preceding year may replace screening study
 
o: when off treatment for reasons other than progression after week 7-8, until week 52.
 
p: Vital signs timepoints for infusions are pre-dose, every 30 minutes; post-dose 30 and 60 minutes (+/- 10 minutes)
 
q: PRO-CTCAE items to be completed at baseline, every 2 weeks for 8 weeks and then every 4 weeks for a total of 8 cycles. All patients on any arm of study will answer the same list of PRO-CTCAE questions.
															

The following visits and assessments are required after discontinuing study treatment:

Days following discontinuation:

30, 60 and 90 days (+/-5 days): physical exam, vital signs, body weight, CBC with diff, serum chemistries^a, pregnancy test for WOCB (urine or serum) AE/SAE assessments, concurrent medications, and performance status.

Table Urinalysis

Urinalysis should be done at baseline (screening) and then as clinically indicated

Bilirubin	Ketones
Blood	pH
Color and appearance	Protein
Glucose	Specific gravity

Note: Microscopy should be used as appropriate to investigate white blood cells and use the high power field for red blood cells.

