5.5 Duration of Follow Up

Patients will be followed for at least 12 weeks after removal from study treatment or until death, whichever occurs first. Patients removed from study treatment for unacceptable adverse event(s) will be followed until progression. All patients will be followed for at least a year from the time of initiation of treatment.

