- If after start of IV methylprednisolone at 2 to 4 mg/kg/day there is no improvement within 3 to 5 days, consider start of immunosuppressive therapy such as TNF inhibitors (e.g., infliximab at 5 mg/kg every 2 weeks). Caution: It is important to rule out sepsis and refer to infliximab label for general guidance before using infliximab.
- Consider whether patient may require IV IG, plasmapheresis.
- Once the patient is improving, gradually taper steroids over ≥ 28 days and consider prophylactic antibiotics, antifungals, or anti-PJP treatment (refer to current NCCN guidelines for

Additional Information:

- ❖ If drugs are given and then patient develops AE before or during radiation, radiation is also held, stopped, unless the treatment field is clearly unrelated to the AE (e.g. liver radiation in a patient who develops pneumonitis), provided the patient is clinically stable for radiation treatment.
- ❖ If either drugs are held then radiation is also held. If all radiation has not been delivered as per protocol, radiation would resume the week following the next drug administration, do not skip.
- ❖ If drugs are held, then any remaining radiation is also held until a week after the next cycle begins, per protocol.
- ❖ If patient experiences an AE, requiring drug hold/discontinuation, both drugs will be held.
- ❖ If drug or radiation is permanently discontinued for toxicity before completion of protocol treatment, the subject would need to come off treatment.

Infusion-Related Reactions		Dose Modifications	Toxicity Management
Severity Grade Any Grade			
 - Management per institutional standard at the discretion of investigator - Monitor patients for signs and symptoms of infusion-related reactions (e.g., fever and/or shaking chills, flushing and/or itching, alterations in heart rate and blood pressure, dyspnea or chest discomfort, skin rashes etc.) and anaphylaxis (e.g., generalized urticaria, angioedema, wheezing, hypotension, tachycardia, etc.)
Grade 1	The infusion rate of study drug/study regimen may be decreased by 50% or temporarily interrupted until resolution of the event		For Grade 1 or Grade 2: 
 - Acetaminophen and/or antihistamines may be administered per institutional standard at the discretion of the investigator - Consider premedication per institutional standard prior to subsequent doses - Steroids should not be used for routine premedication of Grade ≤ 2 infusion reactions.

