13.2.2 Secondary Endpoints

Progression-free survival (PFS): Time from date of randomization until objective disease progression (per RECIST) or death, whichever occurs first. For patients without progression, follow-up will be censored at the date of last adequate restaging, unless death occurs within 12 weeks following the date last known progression-free, in which case the death will be counted as a PFS event.

Overall survival (OS): Time from randomization to death from any cause. For patients lost to follow-up or who have no documentation of death at the time of final analysis, follow-up will be censored at the date of last assessment of vital status.

Objective Response per Immune-Related Response Criteria (irORR): The proportion of patients within a treatment arm who have a best response of irCR or irPR according to Immune-Related Response Criteria. The denominator used to calculate irORR within each treatment will be the

number of patients randomized to the respective treatment arm.

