13.9.2 Evaluation of Response

All patients included in the study must be assessed for response to treatment, even if there are major protocol treatment deviations or if they are ineligible. Each patient will be assigned one of the following categories: 1) complete response, 2) partial response, 3)

stable disease, 4) progressive disease, 5) early death from malignant disease, 6) early death from toxicity, 7) early death because of other cause, or 9) unknown (not assessable, insufficient data). [Note: By arbitrary convention, category 9 usually designates the “unknown” status of any type of data in a clinical database.]

All of the patients who met the eligibility criteria (with the possible exception of those who received no study medication) should be included in the main analysis of the response rate. Patients in response categories 4-9 should be considered to have a treatment failure (disease progression). Thus, an incorrect treatment schedule or drug administration does not result in exclusion from the analysis of the response rate. Precise definitions for categories 4-9 will be protocol specific.

All conclusions should be based on all eligible patients. Subanalyses may then be performed on the basis of a subset of patients, excluding those for whom major protocol deviations have been identified (*e.g.*, early death due to other reasons, early discontinuation of treatment, major protocol violations, etc.). However, these subanalyses may not serve as the basis for drawing conclusions concerning treatment efficacy, and the reasons for excluding patients from the analysis should be clearly reported. The 95% confidence intervals should also be provided.

REFERENCES

References: (Provide references for cited data and key background/concepts. Verify all references.)

1. Siegel, R.L., K.D. Miller, and A. Jemal, *Cancer statistics, 2015*. CA Cancer J Clin, 2015. **65**(1): p. 5-29.
2. Delbaldo, C., et al., *Benefits of adding a drug to a single-agent or a 2-agent chemotherapy regimen in advanced non-small-cell lung cancer: a meta-analysis*. JAMA, 2004. **292**(4): p. 470-84.
3. Hanna, N., et al., *Randomized phase III trial of pemetrexed versus docetaxel in patients with non-small-cell lung cancer previously treated with chemotherapy*. J Clin Oncol, 2004. **22**(9): p. 1589-97.
4. Borghaei, H., et al., *Nivolumab versus Docetaxel in Advanced Nonsquamous Non-Small-Cell Lung Cancer*. N Engl J Med, 2015. **373**(17): p. 1627-39.

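### The imaging instructions conflict, so a patient who stops treatment before week 7-8 may have no post-baseline scan, and the share affected can differ by arm

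*Combined protocol and SAP*

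**What the plan says.** **Calendars (section 10, both cohorts).** The radiologic evaluation row reads "Radiologic measurements should be performed during week 7 or 8 and then every 12 weeks +/- 5 days while on treatment". Its off-treatment column points to footnote o, which provides for scans "when off treatment for reasons other than progression after week 7-8, until week 52". The list of visits after discontinuation is "30, 60 and 90 days (+/-5 days): physical exam, vital signs, body weight, CBC with diff" and further clinical and laboratory items; it contains no imaging. A separate tumour-measurements row reads "Tumor measurements should be performed during week 7 or 8 and then repeated every 12 weeks +/- 5 days", with no on-treatment limit.

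**Section 11.1.** Response is re-evaluated every 12 weeks after a first scan at 7-8 weeks. Being on treatment is not a condition. Responses need a confirmatory scan.

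**Sections 5.5 and 5.6.** "Patients removed from study treatment for unacceptable adverse event(s) will be followed until progression". Section 5.6 runs that follow-up to the later of progression and the minimum follow-up period. All patients are followed for at least a year.

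**Scoring.** Section 13.2.1 classes a missing response as unevaluable and keeps all randomised patients in the ORR denominator. Section 13.9.2 says "All patients included in the study must be assessed for response to treatment" but offers an unknown category and treats categories 4-9 as failures. For PFS without progression, section 13.2.2 says "follow-up will be censored at the date of last adequate restaging", unless death occurs within 12 weeks of the date last known progression-free.

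**Section 6, additional information after the toxicity tables.** "If drug or radiation is permanently discontinued for toxicity before completion of protocol treatment, the subject would need to come off treatment".

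**The concern.** Two schedules can be drawn from the same protocol. A site that follows the radiology row and footnote o may do no scan after baseline in a patient who stops in weeks 1-6. A site that follows the tumour-measurements row or section 11.1 will scan that patient at week 7-8.

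A scan that was never done cannot be recovered at analysis. For ORR, a response that emerges after an early stop would go unseen and count as non-response. For PFS, the last adequate restaging is the pre-treatment one, so the patient leaves the risk set at about time zero. Stopping for toxicity or deterioration is plausibly related to prognosis, so that censoring may be informative.

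The routes to an early stop are not the same in every arm. Stopping radiation for toxicity takes the patient off all treatment, and the NSCLC control arm receives no radiation. Missing scans could therefore be unbalanced in the randomised comparison of the primary endpoint.

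**Working it through.** **1. Two patients under each text**

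| Text | Stops in week 4 for toxicity | Stops in week 30 for toxicity, no progression by week 52 |
|---|---|---|
| Radiology row | no scan (off treatment) | no scan after stopping |
| Footnote o, read as who is scanned | no scan | scans to week 52 |
| Footnote o, read as when scans occur | scans from week 7-8 to week 52 | scans to week 52 |
| Tumour-measurements row, 11.1 | week 7-8, then 12-weekly | 12-weekly |
| 5.5, 5.6 | followed until progression | followed until progression |

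The early gap depends on how footnote o is read. The week-52 stop conflicts with 5.5 and 5.6 on either reading, because RECIST progression cannot be documented without imaging.

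**2. The PFS death window.** Section 10 allows the baseline scan up to 5 weeks before treatment starts. If the date last known progression-free is that scan, the 12-week window can close 12 − 5 = 7 weeks after treatment start. A later death in an unscanned patient would not count as an event.

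**3. The plan's own figures (section 13.4.1).** NSCLC: 5% v 22%, 40 per arm, one-sided 10%, one look at 20 per arm, critical values 2.054 and 1.317, futility below 0.0922. Stated power is 81%. A two-look normal calculation gives 80.3% (pooled variance) or 82.2% (unpooled). Exact binomial enumeration gives 83.4%. Colorectal: at least 1 response in 10, then at least 4 in 30. Exact results are type I error 5.1%, power 81.4% at a 20% rate and early stopping 0.599 under the null, against the stated 5%, 80% and 0.60. The stated figures are reproduced, and this point does not make any of them wrong.

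**4. Sensitivity, under assumptions.** Let a share d have no post-baseline scan, count as non-responders, and otherwise have responded at the arm's planned rate. The observed rate is then p × (1 − d); for d = 10%, 22% becomes 0.22 × 0.90 = 19.8%. The documents do not give d. They report about 13% (section 2.2.1) and 15% (section 2.2.2.1) permanent discontinuation for adverse events on the drug pair, with no time limit stated, so 5-15% is only an illustrative range.

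| d | NSCLC power, both arms affected | NSCLC power, RT arm only | Colorectal power at 20% | Colorectal stage-1 closure at 20%, (1 − 0.20(1 − d))^10 |
|---|---|---|---|---|
| 0 | 83.4% | 83.4% | 81.4% | 10.7% |
| 5% | 81.7% | 80.4% | 78.2% | 12.2% |
| 10% | 79.9% | 77.0% | 74.6% | 13.7% |
| 15% | 77.9% | 73.2% | 70.5% | 15.5% |

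NSCLC entries are exact enumeration with the printed boundaries. No PFS bias figure is offered, because it would rest on hazards that the documents do not contain.

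**The case against.** **The scan is not plainly omitted.** A reader of footnote o alone might infer that early stoppers are never scanned. The documents do not support that. The tumour-measurements row and 11.1 carry the week 7-8 assessment without an on-treatment limit. Section 11.1.4.3 asks sites to try to document objective progression after discontinuation for symptomatic deterioration. Footnote o can itself be read as timing. This stands: the fault is conflicting text. In the text available, the cohort 2 off-treatment mark appears as e, probably a misread o; the footnote wording is the same in both cohorts.

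**13.9.2 does not itself require a scan.** It requires a category, and unknown is one of them. This stands.

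**ORR scoring is settled.** A reader might infer from 11.1.1 that unscanned patients drop out of the ORR. Section 13.2.1 fixes the denominator as all randomised, and 13.9.2 counts unknown as failure. This stands; 11.1.1 needs only a sentence to say that it does not govern.

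**The power figures are soft.** If the planned 5% and 22% already count early stoppers as failures, there is no loss. Patients who deteriorate are unlikely responders, those who withdraw consent cannot be scanned under any calendar, and one scan does not confirm a response. With 5% missing in both arms, exact NSCLC power is still 81.7%, above the stated 81%. The RT-only column presumes excess early toxicity that sections 2.4 and 5.2 do not expect. All of this stands, so the table is illustration only. It does not answer the PFS censoring, the week-52 conflict or the possibility of imbalance.

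**Conclusion.** The imaging instructions are inconsistent and should be reconciled. Followed literally, the radiology row and footnote o can leave a patient who stops before week 7-8, for a reason other than progression, with no post-baseline scan. ORR remains defined, with the patient as a non-responder. PFS is the more exposed endpoint: censoring at about time zero unless death falls in the 12-week window. The week-52 stop contradicts follow-up to progression after an adverse-event stop on any reading.

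The missingness can differ between the NSCLC arms, because only the RT arms can lose patients through radiation toxicity. That it will differ, or that RT will be disadvantaged, is an inference beyond the documents. The size is not given, and any power loss depends on the assumed share, on unscanned patients responding at the planned rate, and on the planned rates not already counting them as failures.

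**What to change.** In both calendars, replace the on-treatment condition and footnote o with one schedule that applies regardless of treatment status: week 7-8, then every 12 weeks, until RECIST progression, death, withdrawal of consent, start of new anticancer therapy or a stated end of follow-up. Make 5.5, 5.6 and 11.1 agree with it.

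In section 13, state that:
- ORR counts only responses seen before new anticancer therapy. Section 5.3 prohibits no therapy in post-treatment follow-up, and 13.2.1 has no such cut-off, so without this rule later-line responses could count.
- The evaluable-for-response definition in 11.1.1 does not define the primary analysis set.
- For PFS, a patient with no post-baseline scan is censored at randomisation unless death falls within the plan's existing 12-week window, counted from randomisation. The window is kept, so that these patients are not given a different death rule from everyone else.

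The cost is calendar and SAP wording, plus a few standard CT scans in off-treatment patients, most of them already implied by 5.5 and 11.1.
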